8.1. Case Record Forms (CRF)

In this study the electronic database and data catching system InCRF will be used. The identity of the participants in the database will be anonymized. The activation key is stored and only to be used by the clinically responsible ophthalmologist. Each study participants are given a study identification number which will be stored in the database. The data manager (DM) and the DM-staff at Meddoc will perform the secondary monitoring on the e-CRFs. Prior to study start, a data entry instruction document will be made. Source data consist of printouts from the laboratory examinations; baseline characteristics; clinical examination collected by the investigator and entered by site. In case of missing data or need of clarification, the responsible monitor will contact the site.

8.2. Study Database

The validated data management system InCRF will be used for collecting the CRF data. The system selected is compliant with GCP guidelines and subject to 21 CFR (Code of federal regulations) FDA part 11 requirements. The final database will be stored in the Statistical Analysis system (SAS ver. 9.4 or later).

8.3: Data handling

A data entry person at site will enter the e-CRF data in InCRF and the DM will perform the initial data validation. In case of missing data, logical errors or interpretation problems, a query will be generated directly in InCRF. Investigator can review the query status via either InCRF function of “Study reports” /” Query report” or patient’s e-Form dashboard. When all the needed participants have finalized the clinical part, and the investigator has electronically signed the e-CRFs, the DM will do the final verification checks and perform final database hard-lock when all errors are corrected.

Screening analysis for logical errors will be evenly performed on this database and errors will be corrected after new information is collected from the site. When all the detected errors are corrected, the main basic database will be locked. The database will be transformed to a labeled SAS database, which also will be locked up to prevent all possible changes or additions. In this copy, the responsible statistician can make derivations but no corrections of the data. If corrections are needed, the main basic study database has to be re-opened and corrected. The international procedure for such changes will be followed.

IX: Discontinuation

A patient may discontinue the study at any time if, in the view of the investigator, it is in the participant's best interests. Alternatively, the participant has the right to discontinue her/his consent and exit the study without prejudice concerning her/his future treatment or care.

If a participant does not show up to an agreed visit, the investigator should try to motivate her/him to continue. However, if the participant has decided not to continue, she/he should be asked to attend a control visit as described for the end of the study (CRF VI).

9.1: Discontinuation not related to the study question

A participant who discontinues the study for administrative reasons or reasons documented not related to the trial equipment classifies as "Drop out" and has to be replaced by a new participant. Such participants will not be included in the statistical analysis.

9.2: Discontinuation related to the study question

Participants discontinue the study for the reasons are related to or might be related to the trial equipment will be classified as "Patient Withdrawal". These participants will not be replaced. They will be included in the Per-Protocol (PP) and the ITT analysis using the "Last-observation-carried-forward" (LOCF) procedure.

X: Ethical consideration

10.1: Consideration of steering committee

The study will be conducted in compliance with the protocol and according to the Helsinki declaration with latest amendments and Good Clinical Practice (GCP).

Participants will only be included in this clinical trial after approval of the trial by the regional Ethical Committee (REK). The patients will receive oral and written information and have to give signed informed consent for participation.

All participants invited to participate in a clinical trial are entitled to make their decision based on the fullest amount of information available at that time. In order to make the choice, they will be given a written document expressed in a clear concise language of their native tongue to consider.

The document will tell potential participants about the nature of the measurements and the equipment. No interventions; only twice BCAM registration per day consecutively in three days. It will outline the numbers of participants in the trial, the steps of the protocol and type of measurements. This will give the participants a clear picture of the risks, inconveniences, and benefits that may accrue from the trial. The participants will be informed that she/he may decline the offer to join the trial or may withdraw at any time without prejudicing further medical care and is covered by the Sponsor's indemnity insurance in the event of mishap. Individuals must also know that their personal hospital records may be reviewed in confidence by the trial appointed research staff and that all personal information will be held on a confidential database. All information in the database will be anonymized and the activation key is stored by the clinically responsible ophthalmologist. Consent must always be given in writing after the participant has had time to reflect on the information and had an opportunity to ask further questions.

BCAM is new equipment, but certificated for clinical use [ISO 13485:2016] and sale in Norway (Appendix 15.2)

BCAM may increase the possibility for the investigator to give a safe diagnose at an early stage; give the final diagnose earlier and follow-up the patients more closely during treatment. However, before using such equipment in clinical practice the validity of the measurements must be documented.

Summary: No results from previous studies with this new equipment indicate any negative effect on the participants and AE has so far never been reported. All participants will be given oral and written information and have to give their written consent to participate in the study. To the best of our knowledge, this study fulfils the entire international requirement to an ethical controlled clinical trial.

10.2: Approval of the project

This study will be performed in Norway and the study protocol together and other requested information will be sent for approval by REK. Inclusion of patients will not be started before the approval is received.

The database and storage will be in Norway and must be approved by the Norwegian center for research data (NSD)

10.3: Informed consent

Before the start of the trial, the investigator will explain the confidentiality of participation in this research project; the objectives of the trial; the specific requirements for the participating patients; the trial design and the consequences of participation. Additionally, the investigators have to obtain written informed consent from the participants before inclusion in the study.

10.4: Protection of personal data

The monitor may know the identity of the patients during verification of the source data.

However, the monitor has unconditional professional secrecy.

All patient-related material leaving the department will be anonymous so that the patient only can be identified by date of birth, initials, and study number.

The investigator is responsible for keeping a list with the full names of the patients, their citizens' number, and corresponding study numbers according to the demands in GCP.

XI: Statistical model

11.1: Handling of discontinuation

All patients fulfilling the inclusion and exclusion criteria, given informed consent to participate and started BCAM registration are classified as included in the study. In the ITT analysis, all these patients will be included and if necessary, the LOCF procedure will be used. The patients classified as Drop-out will be excluded from the statistical analysis.

11.2: Presentation of the result

Assumed continuously distributed variables will be expressed by mean values with 95% confidence intervals.³⁴ As an index of dispersion Standard Deviation (SD) will be used. The agreement index AI defined as $AI = 1 - [SD(X_1 - X_2) / \text{Mean}(X_1 - X_2)]$ will be used for estimation of agreement in continuously variables and expressed by Blend & Altman plot.³⁵ Analysis of variance (ANOVA) with repeated measurements will be used in the analysis of stability.³⁶ In case of skewed distribution, the variable will be tried logarithmic transformed, and the analyses performed on the transformed data. The results will be retransformed for presentation. ANOVA will be used for comparison between patient groups and HC.³⁷ Categorized and discrete distributed variables will be expressed in contingency tables.³⁸ κ -analysis will be performed for estimation of agreement in these variables.³⁹ Additionally, important prevalence will be expressed in percentage with 95% confidence intervals constructed by using the theory of Simple Binomial Sequences.³⁸ Assumed continuously distributed variables will be expressed by mean values with 95% confidence intervals³⁴. As an index of dispersion Standard Deviation (SD) will be used. In case of skewed distribution, the variable will be tried logarithmic transformed, and the analyses performed on the transformed data. The results will be retransformed for presentation. Categorized and discrete distributed variables will be expressed in contingency tables.³⁵ Additionally, important prevalence will be expressed in percentage with 95% confidence intervals constructed by using the theory of Simple Binomial Sequences³⁵.

11.3: Sample size

With a significance level of 5%; a power of 90% and a Clinically Relevant Difference (CRD) of 1xSD between patient groups and HC, at least 16 HC and 16 patients in each diagnose have to be included.

XII: Operational matters

12.1: Investigator's agreement

Before start, the investigators will confirm their agreements to participate in the trial by signing the Investigator's Agreement Form with the Sponsor.

12.2: Instructions

The project manager, supported by the clinical monitor, will instruct the investigators at the start-up visit and during the study.

12.3: Amendments to the protocol

Changes in the protocol can be required by REK, investigators, project manager or Sponsor. Changes must be given in written amendments and numbered in the original protocol. It is forbidden to add new parameters consisting of measurements on the patients in the study unless they are covered as amendments in the protocol or taken due to the health and safety of the patient.

12.4: Protocol deviations

Deviations from the protocol should be restricted as much as possible and will be fully recorded and justified. The project manager will be informed as soon as possible of all protocol deviations.

12.5: Compliance monitoring

The project manager and the investigators will ensure that the site is suitable for the trial and that the participants are well informed of the particular trial. They shall check protocol compliance, handling of the test articles and recording of data during the critical stages of the trial. A report is prepared of each visit and kept in the trial master file (TMF).

12.6: Responsibilities

The investigators will acknowledge their responsibilities and their agreement to participate in the trial by dating and signing the agreement form. The project manager will verify that adequate arrangements have been made for the observations, measurements and recording of the data.

12.7: Confidentiality

This clinical trial is a precondition for further studies in order to obtain permission to market the product worldwide. The Sponsor will therefore use the obtained data and results for the registration of the product. The main study database will be stored in the product database of the Sponsor.

The project manager and the investigators may demand and have the right to have the results published in an international medical journal. The draft of the manuscript has to be presented to the Sponsor for comments, discussion and final approval. The Sponsor cannot stop the

publication unless it is proved that publication of the results may damage the marketing of the product.

The project manager or the investigators cannot present the results in any meeting or congresses without approval by the Sponsor. The data obtained in this study has to be handled confidentially until the first registration of the product is performed.

12.8: Investigator and Sponsor withdrawals

An investigator can finalize his or her participation in the study if BulbiTech A/S does not fulfill its duties according to the protocol or the Sponsor-investigator agreement.

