Sixteen DR patients and 16 AMD patients from each of the two categories will be recruited from the two participating hospitals. All together a total of $16 \times 2 = 32$ patients will be included. For each included patient, one gender- and age-matched HC will be recruited. In total 32 HC.

1.10: Time schedule

The study duration for each participant will be 3 days including six measurements using Bulbicam and one using the Standard method. The recruitment period is nine months. The total duration of the study will be as follows:

Inclusion of the first patient with control	01-05-2022
End of trial; last patient with control	15-01-2023
Closing database	15-02-2023
Finalized Clinical Study Report	01-03-2023

1.11: Flow chart

	Screening	Day 1; Repeatability	Day 2; Stability-1	Day 3; Stability-2
Inclusion and Exclusion criteria	x			
Oral & written informed consent	x			
Patient factors	x			
History of disease	x			
Eye-examination.	x			
Concom. Medicine	x	x	x	x
Quality of Life	x			
Bulbicam tests				
Visual Field		x	x	x
Ptosis		x	x	x
Dynamic Acuity		x	x	x
Dynamic Contrast		x	x	x
Dark Adaption		x	x	x
Pupil		x	x	x
Standard Method				
GAT		x		
ICare		x		
Visual Field		x		
Pupil		x		
OCT RNFL		x		
OCT GCL		x		
Adverse Events [CTCAE]	x	x	x	x
End of study				x

II: Introduction

2.1: Background

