The patients will be recruited from Oslo University hospital, Ullevål and Helgeland hospital. If necessary, private Ophthalmology clinics in Oslo will be asked for recruitment. All the investigations in the study will be performed by the same Ophthalmologist at the given hospital. The investigator informs the patients about the study, handing and collecting the written informed consent form. In case the patient fulfils the inclusion/exclusion criteria and willing to sign the consent form, the patient is included in the study. No data from possible participants included in the screening phase but not fulfils the inclusion/exclusion criteria will be recorded in the database. The included patient will be asked if he/she know any person with same gender and age; in good health condition without any eye disease which may participate as a control in the study. The potential controls will be contacted by the responsible investigator, obtain information about the study, and expected tasks. Controls willing to sign the consent form is included in the study. In case of lack in controls, requests among the hospital staff will be performed.

3.4: Benefit and risk assessment

BulbiCam is new equipment specially developed for clinical investigation of eye. It will simplify neuro-ophthalmic examinations; increase the quality- and benefit of the examinations; detecting earlier correct diagnoses and increase the knowledge of the disease development under treatment. BCAM do not harm neither to the patients nor to the investigator.

IV: Design

4.1: Study design

The study will be performed as a controlled, open and non-randomized, stratified observational multicenter. The two stratification factors will be ophthalmological diagnose and the severity of the disease.

[figure not shown]

Figure 1: The overall study design. The numbers 1 to 6 indicate the sequence of Bulbicam measurements and *) the measurements using the Standard Method

4.2: Stratification

The two main strata are DR and AMD. The patients within each of these two strata will be divided in two sub-strata depending on the disease severity. Within each of the main strata, a third stratum will consist of gender- and age-matched HCs to the patients included in the two other sub-strata.

The three sub-strata within DR will be:

1. Healthy gender- and age-matched controls
2. Mild retinopathy: Mild nonproliferative retinopathy
3. Moderate retinopathy: Moderate nonproliferative retinopathy

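### Section 11.3 claims 90% power for a 1-SD difference with 16 patients and 16 controls per diagnosis; an unpaired two-sided comparison gives about 78%, and 90% needs 23 per group

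*Protocol*

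**What the plan says.** Section 11.3 is the protocol's only justification of the sample size. Its inputs are "With a significance level of 5%; a power of 90% and a Clinically Relevant Difference (CRD) of 1xSD between patient groups and HC", and its conclusion is that "at least 16 HC and 16 patients in each diagnose have to be included". It names no test, does not say whether the test is one- or two-sided, and gives no formula and no correlation.

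Section 11.2 supplies the analysis: "ANOVA will be used for comparison between patient groups and HC". It presents results with 95% confidence intervals.

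The controls are individually matched. Section 1.9 says "For each included patient, one gender- and age-matched HC will be recruited", for 32 patients and 32 HC in total. Section 4.2 places the controls inside each diagnosis, where "a third stratum will consist of gender- and age-matched HCs to the patients included in the two other sub-strata". Neither 11.2 nor 11.3 mentions a paired test.

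**The concern.** The difference is given in SD units, so significance level, power, effect size and group size can be checked against each other without any outside figure. For the simplest reading of the planned comparison, two independent groups tested two-sided, 16 per group is the familiar answer for 80% power, not 90%.

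If the 90% is wrong, a reader of the study report would give too much weight to a non-significant patient-HC comparison, believing that a real 1-SD difference had only a 10% chance of being missed. The stake is bounded. The listed aims are repeatability and stability, comparison with the Standard Method, and a contribution to normal ranges. None of them is a patient-HC hypothesis test.

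**Working it through.** **Inputs.** From 11.3: α = 0.05, target power 0.90, difference δ = 1 SD, 16 patients and 16 HC per diagnosis. From 11.2: ANOVA between patients and HC, which for two groups is the same as a two-sided unpaired t-test. No inflation for drop-out has to be undone, because 9.1 replaces drop-outs. Two-sided and unpaired are my reading; 11.3 states neither.

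**Step 1: trying to reproduce 16.** The normal-approximation formula is n per group = 2(z₁₋α/₂ + z_power)² / δ².

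- 90% power: 2(1.960 + 1.282)² = 21.0, rounded up to 22.
- 80% power: 2(1.960 + 0.842)² = 15.7, rounded up to 16.

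So 16 comes back for 80% power and not for 90%. The protocol does not show how its 16 was obtained.

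**Step 2: exact power at the stated size.** The noncentral t distribution has noncentrality δ√(n/2) and 2n − 2 degrees of freedom. For n = 16 these are √8 = 2.83 and 30, with critical value 2.042.

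| Unpaired, two-sided 5%, 1 SD | Power |
|---|---|
| 16 vs 16 | 78.1% |
| 16 vs 16, ANOVA error pooled over all 64 participants (60 df) | 79.5% |
| 22 vs 22 | 89.97% |
| 23 vs 23 | 91.2% |

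The normal approximation gives 80.7% at 16 vs 16. With 16 vs 16, exact power reaches 90% at a difference of 1.185 SD (1.18 SD gives 89.8%, 1.19 SD gives 90.3%).

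**Step 3: other bases that might explain 16.** The correlations and ICCs below are assumptions; the protocol gives none.

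- *One-sided 5%.* 16 vs 16 gives 86.8%, and 18 per group are needed for 90% (90.2%). The normal approximation gives 88.2% at 16. A one-sided test also does not fit an ANOVA F-test.
- *Matched pairs, SD between participants.* The SD of the pair difference is √(2(1 − ρ)) SD, so the noncentrality is √16 / √(2(1 − ρ)). Sixteen pairs give 75% at ρ = 0, 84% at 0.2, 88% at 0.3 and 93% at 0.4. Power reaches 90% at ρ ≈ 0.34.
- *Matched pairs, SD meaning the SD of pair differences.* 13 pairs give 91.1% and 16 pairs give 96.2%.
- *16 patients against all 32 HC.* 89.2%.
- *Mean of the six registrations, SD meaning that of one registration.* The variance of the mean is ICC + (1 − ICC)/6. Power is 91.8% at ICC 0.60, 88.5% at 0.70 and 85.0% at 0.80, and reaches 90% at about 0.655.

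**The case against.** The strongest reply is that 11.3 names no test, and ANOVA can carry a term for the matched pair, so the word alone does not prove an unpaired analysis. The protocol describes 1:1 matching on gender and age repeatedly. With matched pairs, 16 pairs reach 90% at a moderate correlation. If the SD meant is that of the within-pair differences, 16 is more than enough. On this view the fair charge is an unstated basis, not a true power of 78%.

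Part of this stands. The 78% belongs to the unpaired two-sided reading and is not a statement about every possible analysis. But each reading that rescues the figure needs something 11.3 does not say: a paired test with its correlation, a different meaning of SD, averaged registrations, or a pooled control group. Pooling also falls just short at 89.2% and departs from the 16 HC per diagnosis that 11.3 sets. The pair-difference reading reaches 90% with 13 pairs, so it does not yield 16 as the required number either. Matching in recruitment raises power only if the analysis uses it, and at zero correlation a paired test on 16 pairs does slightly worse (75%) than the unpaired one.

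It also stands that the consequence is limited, because no listed aim rests on this test.

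**Conclusion.** The concern holds. Taken with the ANOVA of 11.2 as an unpaired two-sided comparison, the inputs of 11.3 give 78% power (79% with pooled error), not 90%. The type II error for a 1-SD difference is about 22%, and 90% power needs 23 per group. This rests on the two-sided and unpaired reading. A matched-pair basis could support the stated 90%, but only with a within-pair correlation of about 0.34 or more, or with SD redefined, and the protocol gives neither. The figure should be corrected or its basis stated. Repeatability and stability results are not touched.

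One wording point goes with this. Section 1.9 says "Sixteen DR patients and 16 AMD patients from each of the two categories will be recruited from the two participating hospitals", which can be read as 16 per severity grade, although its own total of 16 × 2 = 32 and section 11.3 both fix 16 per diagnosis.

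**What to change.** Choose one of two corrections to 11.3:

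1. **Correct the figure.** State that 16 patients and 16 HC per diagnosis give about 78% power, two-sided 5% and unpaired, for a difference of 1 SD, or 90% power for about 1.19 SD.
2. **State the basis.** Say that the comparison is matched-pair, define which SD is meant, and give and justify the assumed within-pair correlation (90% needs about 0.34 if the SD is between participants). Section 11.2 would then have to name the paired analysis.

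In 1.9, say plainly that there are 16 patients per diagnosis and 32 in total.

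The cost is a change of wording in 11.3 and 1.9, and in 11.2 under the second option. No participants are added. Under the first option the stated power becomes less favourable. If the sponsor prefers to keep 90% for 1 SD on an unpaired two-sided test, that takes 23 instead of 16 per group: 7 more patients and 7 more HC in each diagnosis, or 4 × 7 = 28 more participants.
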